Stages 3 and 4 constitute the long-term extension portion of the study. Stage 3, which will begin immediately following Stage 2, will include subjects who complete the main treatment period and who are willing to continue with treatment teduglutide 0.05 mg/kg/day SC for up to an additional 24 months. In Stage 4, which will begin immediately following Stage 3, subjects will continue treatment with teduglutide 0.05 mg/kg/day SC in Study TED-C14-004 until teduglutide is commercially available for each subject, the subject's participation in this study is discontinued, or the study is discontinued.

Any subject who achieves complete independence from PN/I.V. support at any time during the Stages 2, 3 or 4 treatment periods will continue to receive teduglutide treatment. If a subject relapses following achievement of PN/I.V. independence, PN/I.V. support will be re-initiated and the subject will continue receiving teduglutide.

A schematic representation of the study design is displayed in [Figure 1](#).

The Schedule of Evaluations and Procedures for each stage are outlined in Section 6.4 of the protocol.

Figure 1 Study Diagram

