5 STATISTICAL/ANALYTICAL ISSUES

6.1 General Methodology

All statistical procedures will be completed using SAS version 9.2 or later.

The small sample size resulting from the small study population requires the use of descriptive statistics with a goal of summarizing the sample and thus discourages the use of inferential statistics. Continuous variables, including those assessed on a discrete scale, will be summarized using descriptive statistics including number of subjects, mean, median, standard deviation, maximum, and minimum. For categorical variables, statistical summaries will include number of subjects and percentages.

For summary purposes, the baseline value will be defined as the last available pre-dose value. Scheduled visits will be summarized as provided in the electronic case report forms (eCRFs). An End of Treatment (EOT) time point, defined as the last determination of endpoint or last available measurement from the date of first dose, will be analyzed in addition to the scheduled visits.

Study Day will be calculated as the date of the evaluation minus the date of the first day of study medication for study days before the first day of study medication, and the date of the evaluation minus the date of the first day of study medication plus one otherwise.

All summaries will be presented by one group, unless otherwise specified. Subjects in the eCRF database who were not treated with study medication will be included in the disposition table as “Enrolled”. For subject data listings, these subjects will be listed in a treatment group specified as ‘Not Treated’.

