8.4 Disposition of Subjects

For the ITT and Safety populations, study enrollment and completion will be summarized by the number and percent of subjects who complete Stages 2, Stage 3, Stage 3 V7 and Stage 4. The number and percent of subjects by the reason for discontinuing each stage early will also be presented.

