13.3 Clinical Laboratory Evaluation

Laboratory parameters will be collected and processed via a central laboratory, SRL, and presented in standard international (SI) units. Clinical laboratory evaluations include the following:

- Chemistry
 - Alanine Aminotransferase
 - Albumin
 - Alkaline Phosphatase
 - Amylase
 - Aspartate Aminotransferase
 - Total Bilirubin
 - Direct Bilirubin
 - Indirect Bilirubin
 - Blood Urea Nitrogen
 - C Reactive Protein
 - Calcium
 - Chloride
 - Total Cholesterol
 - Creatinine
 - Creatinine Clearance
 - Gamma Glutamyl Transferase
 - Glucose
 - Lipase
 - Magnesium
 - Phosphate
 - Potassium
 - Sodium
 - Triglycerides
 - Uric Acid

- Hematology
 - Erythrocytes
 - Hematocrit
 - Hemoglobin

- Leukocytes
- Platelets
- Urinalysis
 - Urine Blood
 - Urine Glucose
 - Urine Leukocytes
 - Urine Microscopic
 - pH
 - Urine Osmolality
 - Urine Protein
 - Urine Sodium

Quantitative results will be summarized for hematology, serum chemistry, and selected urinalysis parameters at each visit collected and at endpoint. Both actual values and change from baseline will be summarized with descriptive statistics defined in Section 6.1.

Additionally, shift tables will be presented for parameters provided by the central laboratory, summarizing cross tabulations of low, normal, and high based on the parameter normal range, from baseline to Week 24, End of Stage 3 and End of Stage 4. Percentages for shift tables will be based on the number of subjects with a value at baseline and at least one post-baseline visit.

Markedly abnormal laboratory values are defined in Table 3. These criteria are based on lab normal ranges and discussions with the experts. The number and percentage of subjects with post-baseline results qualifying as markedly abnormal as defined in this table will be summarized by parameter. A listing will present all values for a subject and laboratory parameter if at least one post-baseline value for that subject and parameter is markedly abnormal.

Table 3 Markedly Abnormal Laboratory Criteria

| Lab parameter | Unit | Lower Limit | Upper Limit |
|----------------------|--------|-------------|-------------|
| Chemistry | | | |
| Albumin | g/L | <=20 | >=90 |
| Alkaline Phosphatase | U/L | NA | >2*ULN |
| ALT | U/L | NA | >3*ULN |
| Amylase | U/L | <=15 | >=350 |
| AST | U/L | NA | >3*ULN |
| Bilirubin (total) | µmol/L | NA | >2*ULN |
| BUN | mmol/L | NA | >=10.7 |
| Calcium (total) | mmol/L | <=2.1 | >=3.0 |

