For summarizations of categorical data, an Unknown or Missing category should be added to any variable for which information is not available for all subjects. However, only the number of unknown or missing subjects will be presented, and percent will be based on non-missing data.

Individual data listings will be sorted and presented by subject number and visit date.

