| Table 14.3.2.13.1 | Details of Adverse Events Leading to Discontinuation - Stage 2 Only | Safety Population |
| Table 14.3.2.13.2 | Details of Adverse Events Leading to Discontinuation - Stage 3 and 4 Only | Safety Population |
| Table 14.3.2.14 | Details of Adverse Events Leading to Death | Safety Population |
| Table 14.3.2.14.1 | Details of Adverse Events Leading to Death - Stage 2 | Safety Population |
| Table 14.3.2.14.2 | Details of Adverse Events Leading to Death - Stage 3 and 4 Only | Safety Population |
| Table 14.3.2.15 | Summary to Treatment Emergent Adverse Events by Time to Onset, System Organ Class, and Preferred Term | Safety Population |
| Table 14.3.2.16 | Summary of Pre-treatment Adverse Events by System Organ Class and Preferred Term | Safety Population |
| Table 14.3.2.17 | Summary of Treatment Emergent Central Line Systemic Infections by Preferred Term | Safety Population |
| Table 14.3.2.17.1 | Summary of Treatment Emergent Central Line Systemic Infections by Preferred Term - Stage 2 Only | Safety Population |
| Table 14.3.2.17.2 | Summary of Treatment Emergent Central Line Systemic Infections by Preferred Term - Stage 3 and 4 Only | Safety Population |
| Table 14.3.3.1 | Summary of Laboratory Values and Change from Baseline by Visit - Chemistry | Safety Population |
| Table 14.3.3.2 | Summary of Laboratory Values and Change from Baseline by Visit - Hematology | Safety Population |
| Table 14.3.3.3 | Summary of Laboratory Values and Change from Baseline by Visit - Urinalysis | Safety Population |
| Table 14.3.3.4 | Summary of Antibody Results by Visit | Safety Population |
| Table 14.3.3.5 | Shift from Baseline to Post-baseline in Clinical Laboratory Parameters by Visit - Chemistry | Safety Population |
| Table 14.3.3.6 | Shift from Baseline to Post-baseline in Clinical Laboratory Parameters by Visit - Hematology | Safety Population |
| Table 14.3.3.7 | Shift from Baseline to Post-baseline in Clinical Laboratory Parameters by Visit - Urinalysis | Safety Population |
| Table 14.3.3.8 | Summary of Post-Baseline Markedly Abnormal Laboratory Values – Chemistry | Safety Population |
| Table 14.3.3.9 | Summary of Post-Baseline Markedly Abnormal Laboratory Values – Hematology | Safety Population |
| Table 14.3.4.1 | Change and Percent Change in 48-hour Fluid Intake from Baseline by Visit | Safety Population |
| Table 14.3.4.2 | Change and Percent Change in 48-hour Urine Output from Baseline by Visit | Safety Population |

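### Laboratory shift-table percentages use an any-visit denominator that does not match the three tabulated time points and conflicts with the SAP's own rule for missing data

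*SAP*

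**What the plan says.** Section 13.3 plans cross-tabulations of low, normal and high against the normal range "from baseline to Week 24, End of Stage 3 and End of Stage 4". The next sentence fixes the denominator: "Percentages for shift tables will be based on the number of subjects with a value at baseline and at least one post-baseline visit". The list of tables in Section 16.1 presents the results by visit, for instance "Shift from Baseline to Post-baseline in Clinical Laboratory Parameters by Visit - Chemistry" (Table 14.3.3.5), with matching tables for hematology and urinalysis, all in the Safety Population.

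Four other places bear on this:

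- Section 6.3 rules out imputation of missing safety parameters.
- Section 15.2, on the format of tables, adds a missing category to categorical summaries and says that "only the number of unknown or missing subjects will be presented, and percent will be based on non-missing data".
- Section 2.1 says that Stage 3 "will include subjects who complete the main treatment period and who are willing to continue with treatment teduglutide"; Stage 4 then follows Stage 3.
- Section 8.4 plans for subjects who leave early: "The number and percent of subjects by the reason for discontinuing each stage early will also be presented".

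**The concern.** The denominator asks whether a subject has a value at any visit after baseline. The table asks where the subject's value lies at one named time point. These are different sets of subjects as soon as someone has no value at that time point. With no imputation, such a subject enters no cell but still adds to the denominator, so the percentages fall short of 100% and each non-empty cell is smaller than the share among those observed.

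The design makes some absence likely. Entry to Stage 3 requires completion of the main period and willingness to continue, so a subject who does not go on still counts in the percentages for the two later time points.

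The rule also conflicts with Section 15.2. Two programmers working from this SAP could produce different percentages for the same table. If Section 13.3 is taken as the specific rule, the shortfall remains, and Section 15.2 gives the missing subjects a count but no percentage that would account for it. Understating shifts is also the less cautious direction in a safety table.

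**Working it through.** The SAP gives no figure to reproduce here. The check is direct arithmetic.

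**Inputs**

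- N: subjects with a baseline value and at least one post-baseline value (the Section 13.3 denominator).
- n: subjects with a baseline value and a value at the tabulated time point.
- x: the count in one cell.
- The SAP gives neither N nor the number absent. Section 2.1 gives a minimum enrolment of 5, so N = 5 is used as an assumption, with N = 7 and N = 10 to show the range. The numbers absent (0 to 3) are also assumed.

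**Formulas**

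- Percentage under Section 13.3: 100 × x/N.
- Percentage among subjects with a value at the time point: 100 × x/n.
- Ratio of the first to the second, for any non-empty cell: n/N.
- Sum of all cells under Section 13.3: 100 × n/N.

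**Results for one shifted subject (x = 1)**

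| N | Absent | n | Cells sum to (13.3) | One shift, 13.3 rule | One shift, denominator n |
|---|---|---|---|---|---|
| 5 | 0 | 5 | 100% | 20.0% | 20.0% |
| 5 | 1 | 4 | 80% | 20.0% | 25.0% |
| 5 | 2 | 3 | 60% | 20.0% | 33.3% |
| 5 | 3 | 2 | 40% | 20.0% | 50.0% |
| 7 | 1 | 6 | 85.7% | 14.3% | 16.7% |
| 7 | 2 | 5 | 71.4% | 14.3% | 20.0% |
| 10 | 1 | 9 | 90% | 10.0% | 11.1% |
| 10 | 2 | 8 | 80% | 10.0% | 12.5% |

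**Illustration across time points.** Assume 5, 4 and 3 subjects present at Week 24, End of Stage 3 and End of Stage 4, all normal at baseline and throughout. The normal-to-normal cell reads 5/5 = 100%, 4/5 = 80% and 3/5 = 60% under Section 13.3. With denominator n it reads 5/5, 4/4 and 3/3, which is 100% each time. The apparent decline comes only from absence.

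When nobody is absent, n = N and the two rules agree. Empty cells are 0% under both.

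**The case against.** The strongest reply is that Section 15.2 already supplies the remedy. Section 13.3 could be read as saying who is eligible for the table, and Section 15.2 as saying how missing entries are handled within it. The shells that would show the denominator are in a separate file. This has some force: it is not certain that diluted percentages would be printed. But Section 13.3 speaks expressly of what the percentages are based on, and the SAP states no order of precedence. What remains is either a denominator that does not fit the table or a conflict between two rules, and the same sentence resolves both.

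Second, the SAP does not define End of Stage 3 or End of Stage 4. Section 11.1 names Week 24 and End of Stage 2 separately, which suggests that an end-of-stage value may be the last one in the stage. A subject who stops during Stage 3 would then still have a value. This stands, and it reduces the expected dilution. It does not help subjects who never enter the stage.

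Third, a constant denominator can be defended: x/N is the share of all evaluable subjects seen with a given shift. That is a coherent quantity, but in a cross-tabulation at a named time point it treats absence as not having shifted.

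Two stronger readings are tempting, and the SAP does not support them:

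- A reader might infer that the three time points cannot be compared under the present rule but could be under the alternative. Yet n varies between time points under the alternative too: with 5, 4 and 3 present, one shifted subject reads 20%, 25% and 33% with no new abnormal finding. Attrition affects both versions.
- A reader might infer that an end-of-treatment shift was left out by mistake, because Section 6.1 says the "last available measurement from the date of first dose, will be analyzed in addition to the scheduled visits". Section 13.3 lists its shift time points explicitly, while its quantitative summary in the same section does include an endpoint. The contrast shows that no such shift is listed, and adding one would be a matter of preference.

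**Conclusion.** The point holds as a mismatch between the stated denominator and the tabulated time points, together with an unreconciled conflict between Sections 13.3 and 15.2. If the Section 13.3 rule is followed, every non-empty cell is scaled by n/N at any time point where values are missing.

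The algebra is exact, but the size rests on assumed numbers: at N = 5 with 1 or 2 absent, cell totals are 80% or 60%. The actual effect depends on attrition and on how the end-of-stage time points are defined, and it may be zero.

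The consequence is minor. The study does no statistical testing, and by-visit summaries, the markedly abnormal tables and the flagged listings carry the laboratory safety information. It is still worth correcting, because reported safety percentages can change and the correction costs almost nothing.

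**What to change.** Replace the denominator sentence in Section 13.3 with wording such as: *At each time point, the denominator for shift percentages is the number of subjects who have both a baseline value and a value at that time point; subjects without a value at that time point are shown as a count.* This brings Section 13.3 into line with Section 15.2.

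The cost is one SAP sentence and the matching denominator in Tables 14.3.3.5 to 14.3.3.7, with no new data. The downside is that the denominator then differs between time points, so n must be printed at each one to let the reader see how many subjects each percentage rests on.

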13.4 Vital Signs

Descriptive statistics (e.g., mean, standard deviation, median, minimum and maximum values, the number and percent of subjects in specified categories) will be used to summarize the vital signs (i.e., sitting systolic blood pressure, sitting diastolic blood pressure, seated pulse rates, body temperature, weight, height, and BMI) by visit and at EOT. Both actual value and change from baseline will be summarized with descriptive statistics defined in Section 6.1.

13.5 ECG Variables

The number and percentage of subjects with each type of ECG finding (Normal/Abnormal, Not Clinically Significant/Abnormal, Clinically Significant) will be presented at Baseline, Week 4, 24, and nominal visits in Stage 3 and Stage 4 will be summarized.

13.6 Physical Examination

Physical examination results will be presented in appendix data listings only. Any clinically significant findings for physical examinations were to be recorded as medical history at screening or as adverse events for all other visits.

13.7 Antibodies to Teduglutide and Escherichia coli Protein (ECP)

A summary table will provide the number of subjects with a sample analyzed for Baseline, Weeks 12, 24, and nominal visits in Stage 3 and Stage 4 will be summarized. The summary table will also provide the number of subjects with an antibody finding at each of those visits.

13.8 Prior and Concomitant Medications

Prior and concomitant medications will be coded to indication-specific ATC (Anatomic Therapeutic Chemical classification) and preferred name using the World Health Organization Drug Dictionary. Investigator verbatim as well as coded terms will be included in the listings.

Prior medications are defined as medications taken prior to the first dose of study medication. Concomitant medications are defined as medications with onset dates on or after the first dose of study medication, medications with onset dates prior to first dose of study medication without a stop date, or medications with a stop date after first dose of study medication. The subject's PN and any components of their PN should not be recorded as a prior or concomitant medication. Partial date imputation for medications is described in Section [6.3](#).

Prior and concomitant medication use will be summarized by preferred name using the number and percentage of subjects. Medications will be sorted alphabetically by ATC and preferred name within ATC. Subjects with multiple occurrences of a medication in ATC and preferred name will only be counted once within each ATC and preferred name. Since medications are coded to ATC by indication, preferred names may appear under multiple ATCs.

A listing of all medications, both prior and concomitant, will be presented. Any abbreviations and codes will be clearly explained on each page of the listing. The listing will be sorted by subject identifier and will include fourth level ATC code, reported name, dose, route of administration, dosing frequency, start date, end date, indication, and period of medication (prior only, concomitant only, prior and concomitant).

13 CHANGES TO THE STATISTICAL METHODOLOGY PRESENTED IN THE PROTOCOL

There are some changes in SAP plan from the protocol as follows;

- PN/IV volume/ calories based on Investigator Prescribed Data will be summarized.
- Binary response to Teduglutide at each visit will be summarized.
- The comparisons with the results of Phase 3 Study CL0600 020, defined in the protocol, will not be performed, and thus will not be included in the clinical study report.

14 GENERAL PROGRAMMING INFORMATION

15.1 General

All programmed table, figure and listing outputs, unless specified otherwise, will be generated using the SAS version 9.2 or later. The programmed outputs will be similar to the format/appearance of the table and listing shells. However, space/formatting limitations may dictate changes in the programmed output. The footnotes specified in the table and listing shells may be changed as necessary for clarifying table entries or the explanation of algorithms or methods used for producing the entries. Significant changes in footnotes will be discussed prior to their implementation.

15.2 Format of Tables/Listings

Tables and listings should be produced in landscape mode and centered horizontally. Required margins are 1 inch for the top, left, right and bottom margins. All output should have a 3-line header at the upper left margin:

Shire
TED-C14-004
Confidential

All output should have a 1-line footer with the SAS program name, including the path, and the date and time the output was produced at the lower left margin of the footer. Tables will have the report listings for the data analyses presented in the table identified at the lower left margin, and listings will have the source eCRF identified.

Tables and listings should be internally paginated in relation to the total length for that table or listing (i.e., Page n of N, where n is the page number within the table or listing and N is the total number of pages for that table or listing).

The table, figure and listing numbering will be based on the International Conference on Harmonization (ICH) guidelines.

A number should identify each table/listing, and the table designation (e.g., Table 1) should be centered above the title. A decimal system (e.g., x, x.y, x.y.z) should be used to identify tables/listings with related contents. The title should be centered and in mixed-case characters. The title and table/listing designation should be single-spaced but are separated from the content of the table/listing by a space and a solid underline. The study population and/or subgroup (e.g., ITT Population) should be identified on the line immediately following the title.

Column headings should be in initial upper-case characters. For numeric variables, the unit should be included in the column heading when appropriate.

Footnotes should be single spaced, but separated by an underline and a space from the text of the table/listing. The notes should be aligned vertically by the left vertical border of the table/listing. Numeric references, which can be confused with data, should not be used. Rather asterisks and other non-numeric symbols should be used to refer to footnotes.

The dictionary (e.g., MedDRA, WHO-DRUG) and the dictionary version numbers should be identified in the footnotes to the tables/listings for data coded with a dictionary.

For summarizations of categorical data, an Unknown or Missing category should be added to any variable for which information is not available for all subjects. However, only the number of unknown or missing subjects will be presented, and percent will be based on non-missing data.

Individual data listings will be sorted and presented by subject number and visit date.

15.3 Data Formats

Unless otherwise specified, means and medians will be rounded and presented to 1 decimal place more than the raw data and standard deviations to 2 decimal places more than the raw data. Minimum and maximum values will be presented to the same number of decimal places as the raw data.

Data in columns will be formatted as follows:

- Alphanumeric values will be center-justified (in mixed upper and lower-case)
- Numerical data will be decimal aligned.
- Fractional data should be presented with the zero to the left of the decimal point (e.g., 0.54).

Unless otherwise specified, percentages should be presented to one decimal place. Less than signs (i.e., '<') should be presented as appropriate (e.g., 0.04% should be presented as < 0.1%, not 0.0%).

Dates will be presented in a DDMONYY format. Dates with partial missing data will be presented with a dash (i.e., '-') for the missing data (e.g., --JAN05).

